8.2.4 Clinical Safety Laboratory Assessments

See [Appendix 2](#) for the list of clinical laboratory tests to be performed and to the schedule of activities (see Section [1.3](#)) for the timing and frequency.

The investigator must review the laboratory report, document this review, and record any clinically relevant changes occurring during the study in the Adverse Event CRF. The laboratory reports must be filed with the source documents. Clinically significant abnormal laboratory findings are those that are not associated with the underlying disease, unless judged by the investigator to be more severe than expected for the participant's condition. A laboratory test result must be reported as an adverse event if it meets any of the following criteria:

- Is accompanied by clinical symptoms

- Results in a change in study treatment (e.g., dosage modification, treatment interruption, or treatment discontinuation)
- Results in a medical intervention (e.g., potassium supplementation for hypokalemia) or a change in concomitant therapy
- Is clinically significant in the investigator's judgment
- ALT or AST > 3 × ULN unless attributed to a specific clinical diagnosis that is to be reported as the primary adverse event term (*see Section 8.3.1 for more information on AE categories*).

Medical and scientific judgment should be exercised in deciding whether an isolated laboratory abnormality should be classified as an adverse event.

All laboratory tests with values considered clinically significantly abnormal during participation in the study or within 4 weeks of the final dose of study treatment should be repeated until the values return to normal or baseline or are *considered to be stable and* no longer considered clinically significant by the investigator. If such values do not return to normal or baseline within a period of time judged reasonable by the investigator, the etiology should be identified and the Sponsor notified.

All protocol-required laboratory assessments, as defined in [Appendix 2](#), must be conducted in accordance with the laboratory manual and the schedule of activities.

If laboratory values from non-protocol-specified laboratory assessments performed at the institution's local laboratory require a change in participant management or are considered clinically significant by the investigator (e.g., serious adverse event or adverse event or dose modification), the results must be recorded on the eCRF. Samples collected for safety laboratory tests will be destroyed no later than the time of completion of the final Clinical Study Report.

8.2.5 Pregnancy Testing

The schedule for pregnancy testing for enrolled female participants is outlined in [Section 1.3](#) and will be conducted as outlined in [Appendix 4](#).

8.2.6 Monitoring for Suicidal Ideation and Behavior

Participants being treated with fenebrutinib should be monitored appropriately and observed closely for suicidal ideation and behavior or any other unusual changes in behavior, especially at the beginning and end of the course of treatment, or at the time of dose changes, either increases or decreases. Consideration should be given to discontinuing the study medication in participants who experience signs of suicidal ideation or behavior, following a risk assessment.

Screening assessment of suicidal ideation and behavior or treatment-emergent suicidal ideation and behavior will be monitored during Study GN43271 using the Columbia-Suicide Severity Rating Scale (C-SSRS).

8.3 ADVERSE EVENTS, SERIOUS ADVERSE EVENTS, AND OTHER SAFETY REPORTING

The definitions of adverse event and serious adverse event can be found in [Appendix 3](#).

Adverse events will be reported by the participant (or, when appropriate, by a caregiver, surrogate, or the participant's legally authorized representative).

The investigator and any qualified designees are responsible for detecting, documenting, and recording events that meet the definition of an adverse event or serious adverse event and remain responsible for following up adverse events that are serious, are considered related to the study treatment or study procedures, or caused the participant to discontinue the study treatment (see Section [7](#)).

8.3.1 Time Period and Frequency for Collecting Adverse Event and Serious Adverse Event Information

After informed consent has been obtained but prior to initiation of study drug, only serious adverse events caused by a protocol-mandated intervention should be reported. The paper Clinical Trial Event/*Special Situations* Form provided to investigators should be completed and submitted to the Sponsor or its designee immediately (i.e., no more than 24 hours after learning of the event), either by faxing or by scanning and emailing the form using the fax number or email address provided to investigators. All other medical occurrences that begin before the start of study treatment but after obtaining informed consent will be recorded on the General Medical History and Baseline Conditions eCRF, not the Adverse Event eCRF.

All adverse events will be reported from the start of treatment until 28 days after the final dose of study treatment at the timepoints specified in the schedule of activities (see Section [1.3](#)).

All serious adverse events will be recorded and reported to the Sponsor or designee immediately and under no circumstance should this exceed 24 hours, as indicated in [Appendix 3](#). The investigator will submit any updated serious adverse event data to the Sponsor within 24 hours of it being available.

Investigators are not obligated to actively seek adverse event or serious adverse event information after conclusion of study participation. However, if the investigator learns of any serious adverse event, including a death, at any time after a participant has been discharged from the study, and he or she considers the event to be reasonably related to the study treatment or study participation, the investigator must promptly notify the Sponsor.

8.3.2 Method of Detecting Adverse Events and Serious Adverse Events

The method of recording, evaluating, and assessing causality of adverse events and serious adverse events and the procedures for completing and transmitting serious adverse event reports are provided in [Appendix 3](#).

Care will be taken not to introduce bias when detecting adverse events and/or serious adverse events. Open-ended and non-leading verbal questioning of the participant is the preferred method to inquire about adverse event occurrences.

8.3.3 Follow-Up of Adverse Events and Serious Adverse Events

After the initial adverse event or serious adverse event report, the investigator is required to proactively follow each participant at subsequent visits or contacts. All adverse events will be followed until the event has resolved to baseline grade or better, the event is assessed as stable by the investigator, the participant is lost to follow-up (as defined in Section 7.3), or the participant withdraws consent. Further information on follow-up procedures is provided in [Appendix 3](#).

8.3.4 Regulatory Reporting Requirements for Serious Adverse Events

Prompt notification by the investigator to the Sponsor of a serious adverse event is essential so that legal obligations and ethical responsibilities towards the safety of participants and the safety of a study treatment under clinical investigation are met.

The Sponsor has a legal responsibility to notify both the local regulatory authority and other regulatory authorities about the safety of a study treatment under clinical investigation. The Sponsor will comply with country-specific regulatory requirements relating to safety reporting to the regulatory authority, Institutional Review Boards or Ethics Committees (IRBs/ECs), and investigators.

For all studies except those utilizing medical devices, investigator safety reports must be prepared for suspected unexpected serious adverse reactions according to local regulatory requirements and Sponsor policy and forwarded to investigators as necessary.

To determine reporting requirements for serious adverse event cases, the Sponsor will assess the expectedness of these events through use of the reference safety information in the document listed below:

Drug	Document
Fenebrutinib	Fenebrutinib Investigator's Brochure

The Sponsor will compare the severity of each event and the cumulative event frequency reported for the study with the severity and frequency reported in the applicable reference document.

Reporting requirements will also be based on the investigator's assessment of causality and seriousness, with allowance for upgrading by the Sponsor as needed.

An investigator who receives an investigator safety report describing a serious adverse event or other specific safety information (e.g., summary or listing of serious adverse events) from the Sponsor will review and then file it and will notify the IRB/EC, if appropriate according to local requirements.

8.3.5 Pregnancy

Female participants of childbearing potential will be instructed through the Informed Consent Form to immediately inform the investigator if they become pregnant during the study or within 28 days after the final dose of fenebrutinib.

Male participants will be instructed through the Informed Consent Form to immediately inform the investigator if a female partner becomes pregnant during the study or within 28 days after the final dose of fenebrutinib.

If a pregnancy is reported, the investigator should inform the Sponsor within 24 hours of learning of the pregnancy and should follow the procedures outlined in [Appendix 4](#).

All pregnancies reported during the study should be followed until pregnancy outcome, with follow-up information on the infant collected according to procedures outlined in [Appendix 4](#). The Sponsor or a designee may follow up by telephone, fax, email, and/or a monitoring visit to obtain additional case details and outcome information (e.g., from hospital discharge summaries, consultant reports, autopsy reports) in order to perform an independent medical assessment of the reported case.

Abnormal pregnancy outcomes (e.g., spontaneous abortion, fetal death, stillbirth, congenital anomalies, ectopic pregnancy) are considered serious adverse events.

8.3.6 Cardiovascular and Death Events

Information on reporting deaths is provided in [Appendix 3](#).

8.3.7 Anticipated Events Not Qualifying for Expedited Reporting

Events not qualifying for expedited reporting will not be defined for this study.

8.3.8 Adverse Events of Special Interest

Adverse events of special interest are required to be reported by the investigator to the Sponsor immediately (i.e., no more than 24 hours after the investigator becomes aware

of the event; see Section A3–5 for reporting instructions). Adverse events of special interest for this study are as follows:

- Cases of potential drug-induced liver injury that include an elevated ALT or AST ($>3 \times \text{ULN}$) in combination with *either an elevated total bilirubin ($>2 \times \text{ULN}$) or clinical jaundice, as defined by Hy's Law (see Section A3–7.6)*
- *Cases of an elevated ALT and/or AST $3\text{--}5 \times \text{ULN}$, $\text{INR} > 1.5$, total bilirubin $\leq 2 \times \text{ULN}$, and absence of clinical jaundice*
- *Cases of elevated ALT and/or AST $5\text{--}8 \times \text{ULN}$, total bilirubin $\leq 2 \times \text{ULN}$ and absence of clinical jaundice*
- *Cases of elevated ALT and/or AST $> 8 \times \text{ULN}$, total bilirubin $\leq 2 \times \text{ULN}$ and absence of clinical jaundice*
- Suspected transmission of an infectious agent by a study treatment, as defined below:

Any organism, virus, or infectious particle (e.g., prion protein transmitting transmissible spongiform encephalopathy), pathogenic or non-pathogenic, is considered an infectious agent. A transmission of an infectious agent may be suspected from clinical symptoms or laboratory findings that indicate an infection in a participant exposed to a medicinal product. This term applies only when a contamination of the study treatment is suspected.

Laboratory results for adverse events of special interest pertaining to hepatic transaminase elevations should be closely monitored, as the AESI category should be upgraded to reflect the most severe liver enzyme results, where required.

8.3.9 Medical Monitors and Emergency Medical Contacts

To ensure the safety of study participants, access to Medical Monitors is available 24 hours per day, 7 days per week. An Emergency Medical Call Center will also be available 24 hours per day, 7 days per week. The Emergency Medical Call Center will connect the investigator with an Emergency Medical Contact, provide medical translation service if necessary, and track all calls. Contact information, including toll-free numbers for the Emergency Medical Call Center, will be distributed to investigators.

8.4 PHARMACOKINETICS

Plasma samples of approximately 9 mL will be collected for measurement of plasma concentrations of fenebrutinib as specified in the schedule of activities (see Section 1.3).

Optional additional intensive PK sample collection will be performed at the Day 1 and Day 29 visits for participants that consent to it. The intensive PK sampling involves collection of blood samples according to the schedule shown in Table 3.

Instructions for the collection and handling of biological samples will be provided by the Sponsor. The actual date and time (24-hour clock time) of each sample will be recorded.

Samples will be used to evaluate the pharmacokinetics of fenebrutinib. Samples collected for analyses of fenebrutinib plasma concentration may also be used to evaluate safety or efficacy aspects related to concerns arising during or after the study.

Genetic analyses will not be performed on these plasma samples. Participant confidentiality will be maintained.

All PK samples will be destroyed no later than 5 years after the final Clinical Study Report has been completed to allow for assay development and validation (if needed).

Information on unblinding of personnel responsible for performing PK assays is provided in Section [6.3](#).

8.5 PHARMACODYNAMICS

Refer to Section [8.7](#) for information on exploratory pharmacodynamic biomarkers.

8.6 GENETICS

Refer to Section [8.10](#) for information on genetic biomarkers.

8.7 BIOMARKER ASSESSMENTS

The following biomarker samples will be collected, as applicable, from participants at all sites:

- Serum and plasma samples for determination of fluid biomarkers of neuronal- and glial *activity*, B cell and myeloid cell *biology*, and the relationship between fenebrutinib exposure and selected pharmacodynamic biomarkers including but not limited to serum and/or plasma neurofilament light chain
- Flow cytometry: Analysis may include, but is not limited to, the determination of B-cell numbers (CD19+) and other lymphocyte subsets

Blood samples for collection of RNA may be measured for exploratory biomarker analyses and may include but not be limited to neuronal- and glial *activity*, B cell and myeloid cell *biology*, and the relationship between fenebrutinib exposure to RNA gene expression. Analyses may involve extraction of RNA for use of next-generation sequencing (NGS) of a comprehensive panel of genes. NGS methods will not include whole genome sequencing (WGS) or whole exome sequencing (WES).

Biomarker samples requiring separate consent are described in Section [8.10](#).

Screening blood samples, including those collected from individuals who do not enroll in the study, may be used for future research and/or development of disease-related tests or tools.

Biomarker samples will be collected according to the schedule outlined in Section 1.3 (see Table 1). Biomarker samples will be sent to one or several central laboratories, academic laboratories or to the Sponsor or a designee. Instructions for the collection and handling of biomarker samples, including sampling procedures, storage conditions, and shipment instructions, are provided in the laboratory manual.

Unless the participant gives specific consent for his or her leftover samples to be stored for optional exploratory research (see Section 8.10) biomarker samples will be destroyed no later than 5 years after the final Clinical Study Report has been completed.

Given the complexity and exploratory nature of exploratory biomarker analyses, data derived from these analyses will generally not be provided to study investigators or participants unless required by law. The aggregate results of any conducted research will be available in accordance with the effective Sponsor policy on study data publication.

8.8 IMMUNOGENICITY ASSESSMENTS

Immunogenicity assessments are not applicable for this study.

8.9 HEALTH ECONOMICS AND MEDICAL RESOURCE UTILIZATION

Health economics and medical resource utilization assessments will not be performed in this study.

8.10 ADDITIONAL ASSESSMENTS AND PROCEDURES REQUIRING SEPARATE CONSENT

8.10.1 Lumbar Punctures and CSF Substudy

Consenting participants will undergo optional lumbar puncture for collection of CSF at the Baseline and Week 12 visits.

The Informed Consent Form will contain a separate section that addresses optional lumbar punctures. The investigator or authorized designee will explain to each participant the objectives, methods, and potential hazards of undergoing optional lumbar punctures. Participants will be told that they are free to choose not to undergo optional lumbar punctures and may withdraw their consent at any time and for any reason. A separate, specific signature will be required to document a participant's agreement to undergo optional lumbar punctures. Participants who choose not to undergo optional lumbar punctures will not provide a separate signature. The investigator should document whether or not the participant has given consent to undergo optional lumbar

punctures and (if applicable) the date of consent, by completing the Sample Informed Consent/Withdrawal eCRF.

[Table 8](#) summarizes CSF substudy PK and biomarker collection during the double-blind treatment phase, according to the schedule outlined in [Section 1.3](#) (see [Table 1](#)). The baseline lumbar puncture can be performed at Day 1 prior to receiving the first dose of study drug, or it can be performed during the screening period prior to Day 1. However, the baseline lumbar puncture should only be performed once other screening tests have been performed and it has been confirmed that the participant qualifies for the study. The lumbar puncture performed at the Week 12 visit should be performed between 1 to 2 hours after the administration of study drug in clinic. At the Week 12 lumbar puncture, a contemporaneous blood sample for PK measurement should be collected at the same time as the lumbar puncture is performed to enable comparison of CSF and plasma drug concentration. *If the Week 12 lumbar puncture is missed, it can be performed at a later visit, including an OLE visit.*

Inflammatory markers in the CSF will be measured as described in [Section 4.2.8](#).

Samples may be used for exploratory biomarker research as described in [Section 8.7](#). For sampling procedures, storage conditions, and shipment instructions, see the laboratory manual. Refer to [Section 8.7](#) for information on duration of sample storage and availability of data from biomarker analyses.

Table 8 Schedule of CSF Substudy Pharmacokinetic and Biomarker Samples for Double-Blind Treatment

Visit	Timepoint	Sample Type
Screening (Day –28 to Day –1) or Day 1 (Week 0) after patient has qualified for study	NA	Biomarkers (CSF, serum ^a)
Day 85 (Week 12)	1-2 hours after dosing	PK (CSF, plasma), biomarkers (CSF, serum)

CSF = cerebrospinal fluid; NA = not applicable; PPI = proton pump inhibitor;
PK = pharmacokinetic

^a Sample will come from the main study in order to avoid duplication. This is not an additional sample to the main study

Notes:

- Morning clinic visits are preferred for all visits but are required on Day 1. Prior to each morning clinic visit, participants should be instructed not to take their morning dose and to bring their study medication with them to their clinic visit. The dates and times of the last dose of oral study drug (prior to the clinic visit) and timing of oral study drug administration in the clinic should be recorded at each clinic visit. Use of PPIs, H₂-receptor antagonists, and/or other antacids (e.g., bismuth subsalicylate, calcium carbonate, aluminum-magnesium hydroxide) should be recorded as concomitant medications, including the date and time of last administration at each clinic visit.
- Single-dose acid-reducing agents are not permitted on the day of an in-clinic visit with PK assessments.
- At Week 12, PK CSF and plasma samples should be taken contemporaneously when feasible.

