- ° Tests required for hepatitis B screening: HBsAg, total HBcAb, and viral DNA PCR. Participants with a positive HBsAg must be excluded. Participants with a positive HBcAb are permitted provided viral DNA PCR is negative. Participants with a positive HBcAb but negative HBV DNA PCR will have their hepatitis B viral DNA monitored as per the schedule of activities.
- ° Hepatitis C screening: HCAb must be negative.
- ° Please refer to [Table 3](#) for more details.
- ° Biomarker samples should be collected ± 3.5 days from MRI scan. Note: Not all biomarker samples will be collected at each MRI visit; however, those that are collected should be collected as close to the MRI scan as possible.
- ° All women of childbearing potential will have a serum pregnancy test at screening. Urine pregnancy tests will be performed at specific subsequent visits. If a urine pregnancy test is positive, it must be confirmed by a serum pregnancy test.
- ° The Day 1 CSF collection by lumbar puncture should only be performed once other screening tests confirm that the patient qualifies for the study. Lumbar puncture can be performed anytime during the screening period or at Day 1 prior to dosing. The Week 12 lumbar puncture should to be performed between 1 to 2 hours after the administration of study drug in clinic. A contemporaneous plasma PK sample should be collected at the time of CSF collection to enable comparison of CSF and serum drug levels. *If the Week 12 lumbar puncture is missed, it can be performed at a later visit, including an OLE visit.*
- ° MRI scans should be obtained as close to the scheduled visit as possible (± 3 days) and may be obtained at UV if medically warranted. MRI scan may not be performed earlier than 3 weeks after IV corticosteroid treatment for MS relapses. At the study D/C visit, an MRI scan should be obtained if an MRI scan was not performed during the prior 4 weeks.
- ° Study treatment will only be dispensed for participants continuing in the optional OLE.
- ° RBR: Not applicable at a site that has not been granted approval for RBR sampling. Performed only for patients at participating sites who have provided written informed consent to participate.
- ° A single, DNA sample will be collected for RBR at the baseline visit. If the DNA sample is not taken at Visit 2 (baseline), the sample may be taken at any subsequent timepoint during the trial.

Table 2 Schedule of Activities: Open-Label Extension Phase

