#### **5.5.1.3 CSF IgG Index and Oligoclonal Bands (CSF Sample is Optional)**

Change from baseline of IgG Index may be summarized descriptively by visits. The LS mean of placebo adjusted treatment effect of fenebrutinib may be estimated by a MMRM model at Week 12.

Change from baseline of CSF IgG Oligoclonal Band status (positive/negative) may be summarized descriptively by visits.

Change from baseline of Albumin Index may be summarized descriptively by visits. The LS mean of placebo adjusted treatment effect of fenebrutinib may be estimated by a MMRM model at Week 12.

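### For a screening-period lumbar puncture, nothing ties the baseline serum to the puncture day, which can add noise to change in IgG and albumin index

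*Protocol*

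**What the plan says.** - **Purpose and size.** Protocol Section 4.2.8 plans CSF from roughly 10 participants at two timepoints and describes the IgG index as a CSF-to-serum measure.
- **Baseline puncture.** The lumbar puncture footnote to Table 1 states: "Lumbar puncture can be performed anytime during the screening period or at Day 1 prior to dosing". Section 8.10.1 sets the order: "the baseline lumbar puncture should only be performed once other screening tests have been performed", with eligibility confirmed.
- **Baseline serum.** The baseline row of Table 8 lists CSF and serum biomarkers with the timepoint marked not applicable. Footnote a on the serum reads: "Sample will come from the main study in order to avoid duplication. This is not an additional sample to the main study".
- **Main-study serum.** Before dosing, Table 1 schedules serum biomarkers at screening and at Week 0 (predose). Their timing is set by the scan: "Biomarker samples should be collected ± 3.5 days from MRI scan".
- **Week 12.** Table 8 lists CSF and serum biomarkers on one row at 1 to 2 hours after dosing, and this serum carries no footnote a. A missed puncture may move to a later visit, including one in the open-label extension.
- **Analysis.** SAP Section 5.5.1.3: "Change from baseline of IgG Index may be summarized descriptively by visits". The albumin index is treated the same way, and both may have an MMRM estimate at Week 12.

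**The concern.** Both indices divide a CSF value by a serum value. If the two fluids are drawn on different days, any change in serum between those days enters the ratio. For a screening-period puncture the Protocol has no rule that puts them on one day, whereas the Week 12 row does list them together. Change from baseline could then subtract a loosely paired ratio from a closely paired one. What is at stake is precision in a very small, optional dataset.

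**Working it through.** The documents give no figure for these indices, so there is none to reproduce. The check has two parts.

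**1. The gap that the schedule allows** (Tables 1 and 8; there is no Day 0)

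- Serum on Day -28, puncture on Day -1: -1 - (-28) = 27 days.
- Puncture on Day -28, serum on Day 1: 28 days.
- Puncture on Day 1: 0 days, because a predose tube is scheduled that day.
- Week 12: the same 1 to 2 hour window.

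Re-screening can lengthen the first gap, since Table 1 footnote a asks for biomarker samples to be repeated only after more than 6 weeks. I take the index serum to be the serum biomarker tube, as Table 8 labels it. If SAP Section 5.7.2's last-value definition of baseline were applied to the serum, it would select the Day 1 tube even when the CSF came from screening.

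**2. What the gap could cost** (all inputs are assumptions; none is in the documents)

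Assumed definitions: IgG index = (CSF IgG / serum IgG) / (CSF albumin / serum albumin); albumin index = CSF albumin / serum albumin.

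Assumed inputs:

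- CV, the between-day within-person variation of each serum analyte: 3% to 5%.
- s, the SD of change in log index with same-day pairs: 0.10 to 0.20.
- f, the share of punctures done in screening: 0 to 1.
- rho, the correlation between day-to-day shifts in serum IgG and serum albumin: 0 to 0.5.
- CSF reflects same-day serum.

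Using serum from another day adds two independent daily deviations, so 2 CV² per analyte. In the IgG index the two analytes enter with opposite signs, so shared shifts cancel. The variance of the change is multiplied by:

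- IgG index: 1 + 4 f (1 - rho) CV² / s²
- Albumin index: 1 + 2 f CV² / s²

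The equivalent loss of participants is 10 × (1 - 1/factor).

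| Index | CV | s | f | rho | Factor | Loss of 10 |
|---|---|---|---|---|---|---|
| IgG | 0.05 | 0.10 | 1 | 0 | 1 + 0.0100/0.0100 = 2.0 | 5 |
| IgG | 0.05 | 0.10 | 0.5 | 0 | 1.5 | 3.3 |
| IgG | 0.05 | 0.10 | 1 | 0.5 | 1.5 | 3.3 |
| IgG | 0.05 | 0.10 | 0.5 | 0.5 | 1.25 | 2 |
| IgG | 0.03 | 0.20 | 1 | 0 | 1 + 0.0036/0.0400 = 1.09 | 0.8 |
| Albumin | 0.05 | 0.10 | 1 | n/a | 1 + 0.0050/0.0100 = 1.5 | 3.3 |
| Albumin | 0.03 | 0.20 | 1 | n/a | 1 + 0.0018/0.0400 = 1.045 | 0.4 |
| Either | any | any | 0 | any | 1.0 | 0 |

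The assumption that CSF reflects same-day serum matters most. If CSF instead tracks a multi-day serum average, a same-day tube and another-day tube carry about the same noise, and the factor is about 1.0 whatever the other inputs. The value 2.0 is the top of these assumed ranges, not a mathematical bound.

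For scale: if the 10 participants split 2:1, the between-arm difference detectable with 80% power at two-sided 0.05 is about 2.80 × √(1/3.33 + 1/6.67) = 1.88 SD (normal approximation), even with perfect pairing.

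**The case against.** The strongest reply is that the present text already permits good practice. Screening is a window, and nothing forbids drawing the main-study tube at the puncture. Section 8.10.1 leaves sampling procedures to the laboratory manual, which is not available here. The same section places the punctures at the Baseline and Week 12 visits, and the Table 1 footnote calls the first one the Day 1 collection, so most may be on Day 1. Footnote a is also a deliberate choice to spare participants a duplicate sample. The endpoints are optional and exploratory, and no decision rests on them.

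Most of this stands, and it limits the point to a small one. It does not remove it: the Protocol allows a screening puncture, sources its serum from a tube timed to the MRI, and sets no limit on the gap.

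A reader might go further in five ways that the documents do not support:

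- *Baseline serum is normally drawn on another day.* This is only an inference from the eligibility-first rule. No text fixes the day, and the share of screening punctures is not given.
- *The comparison between arms is biased.* The mismatch arises before dosing in both arms, so noise is expected, not bias.
- *Half of the substudy's information is lost.* That needs the highest CV, the smallest SD, every puncture in screening, independent IgG and albumin shifts, and CSF that follows same-day serum.
- *Oligoclonal bands are affected too.* The SAP summarises band status as positive or negative, and nothing shows that serum variation of a few percent would alter it.
- *The Week 12 index pairing is also loosened by the Table 8 note.* That note concerns PK plasma, not the index serum, and it does not say that the sample may be skipped.

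The Week 12 contrast itself needs care. Same-time serum there is read from a shared table row, since the explicit same-time wording covers the PK blood sample only.

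**Conclusion.** The point holds for screening-period punctures only. Their baseline CSF is paired with serum that neither document ties to the puncture day, with an allowed gap of up to about 4 weeks, while Table 8 lists Week 12 CSF and serum together. This can add noise, without expected between-arm bias, to change from baseline in IgG and albumin index in about 10 participants.

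The size is unknown. Under the assumptions above, the variance factor runs from about 1.0 to at most 2.0 for the IgG index and 1.5 for the albumin index. It is smaller if serum IgG and albumin shift together (IgG index) or if only some punctures fall in screening (both). No primary or secondary analysis is touched. The change is worth making because it is cheap and these participants accept a lumbar puncture to provide the data.

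**What to change.** 1. **Table 8 footnote a.** For a screening-period puncture, draw the already scheduled screening serum biomarker tube on the day of the puncture. For a Day 1 puncture, use the Day 1 predose tube.
2. **SAP Section 5.5.1.3.** State that the indices are computed from same-day CSF and serum pairs.
3. **Moved Week 12 puncture.** Apply the same rule, with serum drawn on the day of the puncture.

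The baseline change needs no extra tube or visit: the serum biomarker tube is not an eligibility test, so it can wait for the puncture. The Day 1 predose tube stays the main-study biomarker baseline under the last-value definition. The downside is that the screening tube may fall outside the ±3.5-day MRI window in about 10 participants. A moved Week 12 puncture needs either a visit that already has a serum biomarker tube (in Table 2, for example, Weeks 12 and 24) or one added tube.

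Separately, and without bearing on the indices, the two statements on the Week 12 PK plasma sample should be reconciled. Section 8.10.1 says "a contemporaneous blood sample for PK measurement should be collected at the same time as the lumbar puncture is performed"; the Table 8 note says "At Week 12, PK CSF and plasma samples should be taken contemporaneously when feasible".
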